7.5 Diagnostic Efficacy Assessments

7.5.1 Assessment of the Composite Reference Standard

The composite Reference Standard may consist of histopathology, conventional imaging modalities that are routinely used in the diagnosis and staging of PC and PSA levels. ⁶⁴Cu-SAR-bisPSMA scans will not form part of the Reference Standard.

The Reference Standard status will be determined by an independent, blinded, central expert panel. The expert panel will establish the Reference Standard disease status (on a participant-and region-level) for each participant individually, using information provided by the site's Investigator. The experts will be blinded as described in Section 4.3.

The Investigator will be required to submit all relevant clinical evidence available for the participant to enable the assessment of the Reference Standard. Relevant evidence will include:

- All available histopathology reports related to the participants disease history;
- All available conventional scans and related local reports collected as part of Screening (within 60 days of Day 0) and Follow-up (within 180 days [±15 days] of Day 0);
- PSA levels recorded as part of Screening and Follow-up;
- All available PC related symptom and treatment history;

The composite Reference Standard will be hierarchical in nature, with three levels of evidence that will be applied as follows:

- Level 1: Evaluable histopathology from biopsy or surgery OR in case that histopathology is not available, inconclusive or negative:
- Level 2: Conventional imaging procedures OR if neither histopathology or conventional imaging are available or informative:
- Level 3: Confirmed PSA response following radiation or other salvage focal therapy (as long as no concomitant ADT is given), defined as total PSA decline by ≥50% from baseline, confirmed by a second value within four weeks as per the Prostate Cancer Working Group 3 criteria²⁵.

The expert panel will use the collective information to determine and record each region with histopathology demonstrating PC, the number of lesions suspicious for PC detected on conventional imaging in each anatomical subregion and whether the participant achieved confirmed PSA response (if applicable).

Region(s) with no histopathology demonstrating PC or no unequivocal lesion recorded in any of the anatomical subregions on conventional imaging will be deemed negative for the region level Reference Standard status.

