7.5.2 Assessment of Reference Standard against the ⁶⁴Cu-SAR-bisPSMA PET/CT Results

For the assessment of the Reference Standard against the ⁶⁴Cu-SAR-bisPSMA PET/CT, region-level matching will be used for histopathology, subregion-level matching for imaging and participant-level matching for PSA response to radiation or other salvage focal therapy (refer to Section 7.5.1). Matching of the Reference Standard against the ⁶⁴Cu-SAR-bisPSMA PET/CT results will be completed via statistical programming.

Assessment of **region-level** Reference Standard against the ⁶⁴Cu-SAR-bisPSMA PET/CT results:

- Histopathology: A region that is ⁶⁴Cu-SAR-bisPSMA PET-positive (i.e., includes at least one unequivocal PET-positive lesion) and Reference Standard positive, will be assigned as true positive (TP) for the region-level status.
- Imaging: A subregion that is ⁶⁴Cu-SAR-bisPSMA PET-positive (i.e., includes at least one unequivocal PET-positive lesion) and Reference Standard positive (i.e., includes at least one unequivocal lesion detected on conventional imaging in that subregion), will be assigned as TP. A region that includes at least one TP subregion will be assigned as TP for the region-level status.
- A region that is ⁶⁴Cu-SAR-bisPSMA PET-positive (i.e., includes at least one unequivocal PET-positive lesion) and is Reference Standard negative based on at least 1 evaluable timepoint, will be assigned as false positive (FP) for the region-level status.
- A region that is ⁶⁴Cu-SAR-bisPSMA PET-negative (i.e., no unequivocal PET-positive lesion or only equivocal lesion(s) detected within the subregions) and Reference Standard negative, will be assigned as true negative (TN) for the region-level status.
- A region that has either non-evaluable ⁶⁴Cu-SAR-bisPSMA result for a specific timepoint or has a non-evaluable or inconclusive Reference Standard will not be assigned for that timepoint.

Assessment of **participant-level** Reference Standard against the ⁶⁴Cu-SAR-bisPSMA PET/CT results:

- A participant with at least one TP region AND/OR at least one unequivocal ⁶⁴Cu-SARbisPSMA PET-positive lesion and confirmed PSA response to radiation or other salvage focal therapy, will be assigned as TP for the participant-level status.
- A participant with at least one unequivocal ⁶⁴Cu-SAR-bisPSMA PET-positive lesion who does not meet the above criteria to be deemed TP, will be assigned as FP for the participant-level status.

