10.4.5.1 Primary Efficacy Analyses

The co-primary efficacy endpoints include the following:

- Participant-level CDR on Day 0 scan;
- Participant-level CDR on Day 1 scan;
- Region-level PPV on Day 0 scan;
- Region-level PPV on Day 1 scan.

CDR on a participant-level for each central reader is defined as the proportion of TP participants out of all scanned participants who had at least 1 evaluable reference standard datapoint (as without any follow-up reference data it is not possible to determine if the participant is TP or not, which may bias the results) and will be calculated as follows: CDR = TP/(all scanned participants with at least 1 evaluable reference datapoints).

Participants without a ⁶⁴Cu-SAR-bisPSMA PET/CT scan at a specific timepoint (Day 0 or Day 1) will be excluded from the participant-level CDR calculation for that timepoint. Participants with non-evaluable participant-level Reference Standard results will be excluded from the CDR calculation.

PPV on a region-level for each central reader is defined as the proportion of TP regions out of all positive regions on the ⁶⁴Cu-SAR-bisPSMA PET/CT scan with corresponding evaluable composite Reference Standard data and will be calculated as follows: PPV = TP/(TP+FP).

Regions that are not positive on the ⁶⁴Cu-SAR-bisPSMA PET/CT scan at a specific timepoint (Day 0 or Day 1) will be excluded for the region-level PPV calculation for that timepoint.

Region	Description of Anatomic Region
1	Prostatic
2	Pelvic lymph nodes
3	Extra pelvic lymph nodes
4	Visceral/soft tissue
5	Bone

The anatomic regions for lesions include the following:

The point estimates of CDR and PPV on Day 0 and on Day 1 will be computed along with the 2-sided 95% exact binomial CIs using the Clopper-Pearson method. The primary efficacy analyses will be performed for each central reader.

The following sensitivity analyses of the participant-level CDR and region-level PPV will be performed:

- •
- Based on all participants in the FAS regardless whether there are reference datapoints collected. Missing data will be handled as follows:
 - Worst-case imputation:
 - For the participant-level CDR on Day 0 and on Day 1 based on FAS, participants with missing/non-evaluable composite Reference Standard data will be imputed as non-true positive and included in the denominator.

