## 4.2 Sample Size Estimation

Approximately 50 participants are planned to be enrolled into the study. The assumed CDR of Cu-SAR-bisPSMA PET/CT imaging is 42% in this population. A sample size of 40 participants is estimated to provide more than 85% power to achieve a lower boundary of a 2-sided 95% exact binomial confidence interval (CI) about the estimated CDR that exceeds 20%. Accounting for a 20% non-evaluable rate, approximately 50 participants will need to undergo Cu-SAR-bisPSMA PET/CT in this study.

Additionally, for the co-primary efficacy endpoint of region-level PPV, assuming 65% of participants are estimated to have Cu-SAR-bisPSMA PET/CT positive findings in this target population and each participant with positive findings has an average of 1.3 positive regions, then 40 participants are expected to produce approximately 34 positive regions. The assumed region-level PPV rate of Cu-SAR-bisPSMA PET/CT imaging is approximately 65% in all PET positive regions. Therefore, a sample size of 40 participants (i.e., approximately 34 positive regions) is

September 4, 2024 CONFIDENTIAL Page 14 of 46

estimated to provide more than 80% power to achieve a lower boundary of a 2-sided 95% exact binomial CI about the estimated region-level PPV that exceeds 40%.

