## • True Positive:

- Histopathology: A region that is Cu-SAR-bisPSMA PET-positive (includes at least one unequivocal PET-positive lesion) and Reference Standard positive is considered a TP region.
- o Imaging: A subregion that is Cu-SAR-bisPSMA PET-positive (i.e., includes at least one unequivocal PET-positive lesion) and Reference Standard positive (i.e., includes at least one unequivocal lesion detected on conventional imaging in that subregion) is considered a TP subregion. The subregion must match between the two assessments. If any region has at least one TP subregion, the region-level status is considered TP.

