#### • False Positive:

 A region that is Cu-SAR-bisPSMA PET-positive (i.e., includes at least one unequivocal PET-positive lesion) and Reference Standard negative based on at least 1 evaluable timepoint.

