#### 9.14.1 Primary Efficacy Analyses

The co-primary efficacy endpoints are the following:

- Participant-level CDR at Day 0.
- Participant-level CDR at Day 1.
- Region-level PPV at Day 0.
- Region-level PPV at Day 1.

September 4, 2024 CONFIDENTIAL Page 28 of 46

 $\underline{CDR}$  on a participant-level for each central reader is defined as the proportion of TP participants out of all scanned participants who had at least 1 evaluable reference standard datapoint collected and is calculated as:  $\overline{CDR} = \overline{TP}/(all\ scanned\ participants\ with at least 1 evaluable reference datapoint) x 100.$ 

Participants without a Cu-SAR-bisPSMA PET/CT scan at the specific timepoint (Day 0 or Day 1) will be excluded from the participant-level CDR calculation for that timepoint. Participants with non-evaluable participant-level Reference Standard results will be excluded from the CDR calculation

PPV is measured on a region-level (the primary endpoint will be calculated including all 5 regions as a whole) for each central reader and is defined as the proportion of TP regions out of all positive regions on the  $^{64}$ Cu-SAR-bisPSMA PET/CT scan with corresponding evaluable composite Reference Standard data and will be calculated as: PPV = TP/(TP + FP) x 100, where FP = False Positive.

Regions that are not positive on the Cu-SAR-bisPSMA PET/CT scan at a specific timepoint will be excluded from the region-level PPV for that timepoint. PET/CT positive regions without corresponding evaluable composite Reference Standard results will also be excluded.

The anatomic regions for the PPV calculation are the following:

- Region 1 = Prostatic
- Region 2 = Pelvic lymph nodes
- Region 3 = Extra pelvic lymph nodes
- Region 4 = Visceral/soft tissue
  - o This region is incorrectly labeled as Region 5 in the raw data and will be recoded
- Region 5 = Bone
  - o This region is incorrectly labeled as Region 4 in the raw data and will be recoded

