## 9.14.2 Secondary Efficacy Analyses

The following secondary analyses will be performed in a similar manner as the primary analysis, and will be summarized by central reader with point estimates and exact Clopper-Pearson 95% CI in the FAS and repeated with the PP analysis set:

- Participant-level PPV at Day 0 and Day 1;
  - $\circ$  PPV = TP/(TP + FP) x 100.
- Participant-level Detection Rate (DR) at Day 0 and Day 1;
  - o DR = (number of participants with positive Cu-SAR-bisPSMA PET/CT scan)/(all scanned participants with a Cu-SAR-bisPSMA PET/CT scan) x 100.

September 4, 2024 CONFIDENTIAL Page 30 of 46

- Participant-level False Positive Rate (FPR) on Day 0 and Day 1;
  - $\circ$  FPR = FP/(all scanned participants with a positive Cu-SAR-bisPSMA PET/CT scan and an evaluable reference standard) x 100.
- Region-level FPR at Day 0 and Day 1;
  - $\circ$  FPR = FP regions/(all positive regions on the Cu-SAR-bisPSMA PET/CT scan and an evaluable reference standard) x 100.
- Participant-level discrepant PET negative rate between Day 0 and Day 1 for reference standard positive participants.
- Discrepant PET negative rate;
  - O Discrepant PET negative rate = (number of participants with participant-level discrepancy in Cu-SAR-bisPSMA results between Day 0 and 1) / (all participants with a positive reference standard) x 100.
- Participant-level True Negative Rate (TNR) on Day 0 and Day 1;
  - $\circ$  TNR = TN/(TN+FP) x 100.
- Participant-level Apparent Negative Predictive Value (ANPV; referred to as TNR in the study protocol) on Day 0 and Day 1;
  - o TN/(number of participants with a negative Cu-SAR-bisPSMA result)
- Region-level TNR at Day 0 and Day 1.
  - $\circ$  TNR = TN/(TN+FP) x 100.
- Region-level Apparent Negative Predictive Value (ANPV; referred to as TNR in protocol) at Day 0 and Day 1;
  - o TN/(number of regions with a negative Cu-SAR-bisPSMA result).

Note: Discrepant Day 0 and Day 1  $^{64}$ Cu-SAR-bisPSMA PET/CT results (results differ within subregion from Day 0 and Day 1 within the same central reader) will also be listed.

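### A PET-positive region whose only reference lesion is on imaging in a different subregion has no class in SAP 7.8, so the wording and the formula of the co-primary region-level PPV disagree.

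*SAP*

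**What the plan says.** **Region classes (SAP 7.8; Protocol 7.5.2).** Histopathology is matched at region level and imaging at subregion level. For imaging the SAP adds: "The subregion must match between the two assessments". The Protocol then builds the region from its subregions: "A region that includes at least one TP subregion will be assigned as TP for the region-level status". A false positive region must be PET-positive "and Reference Standard negative based on at least 1 evaluable timepoint". True Negative and Test Negative both require a negative PET. Non-evaluable requires a non-evaluable PET, or a non-evaluable or inconclusive reference.

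**Reference status (Protocol 7.5.1).** Positive histopathology makes the region positive. An unequivocal imaging lesion makes its subregion positive. For negative status: "Region(s) with no histopathology demonstrating PC or no unequivocal lesion recorded in any of the anatomical subregions on conventional imaging will be deemed negative".

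**Endpoint (Protocol 10.4.5.1; SAP 9.14.1).** In the Protocol's words: "PPV on a region-level for each central reader is defined as the proportion of TP regions out of all positive regions on the" PET/CT scan, restricted to regions with evaluable reference data. The SAP wording has the same restriction and continues: "with corresponding evaluable composite Reference Standard data and will be calculated as: PPV = TP/(TP + FP) x 100, where FP = False Positive".

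**Related places.** Region-level FPR in SAP 9.14.2 is "FPR = FP regions/(all positive regions on the" scan that also have an evaluable reference. SAP 4.2 sizes this endpoint on a PPV that for PET/CT "imaging is approximately 65% in all PET positive regions".

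**The concern.** The region-level classes do not cover every PET-positive region with an evaluable reference. The uncovered case is a PET lesion in one subregion while the only reference lesion is on imaging in another subregion of the same region. The wording and the formula of PPV then give different denominators for a co-primary endpoint.

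If the formula and the FP rule are programmed as written, these regions disappear from PPV and the estimate rises above the worded definition. They are PET calls that the reference did not confirm at the level of matching the plan requires. The worst-case and tipping-point analyses in SAP 9.14.1.1 deal only with missing, non-evaluable or inconclusive reference data, so they would not show the effect. PPV is also reported for each region separately (SAP 9.14), where denominators are smaller and one dropped region shifts the estimate more.

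**Working it through.** **1. Classify the example.** Pelvic lymph nodes: PET-positive in Left Pelvic, no positive histopathology, and the only unequivocal reference lesion on imaging in Right Pelvic.

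| Class | Requirement | Met? |
|---|---|---|
| TP, histopathology | positive histopathology in the region | no |
| TP, imaging | same subregion | no |
| FP | region reference-negative | no: a lesion is recorded in one of its subregions |
| TN, Test Negative | negative PET | no |
| Non-evaluable | non-evaluable PET, or non-evaluable or inconclusive reference | no |

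The case cannot arise in Prostatic, which has one subregion (SAP Table 2). The other four regions have 3 to 13. The composite rules in SAP 9.14.3.1 resolve it only if the region is TP on the other day.

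**2. Reproduce the plan's sizing.** Inputs from SAP 4.2: 40 participants, 65% PET-positive, 1.3 positive regions each, PPV 65%, lower bound above 40%.

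- Positive regions: 40 × 0.65 × 1.3 = 33.8, about 34.
- The smallest TP count out of 34 with a Clopper-Pearson 95% lower bound above 40% is 20 (20/34: 40.7%; 19/34: 37.9%).
- P(TP ≥ 20 | n = 34, p = 0.65) = 82.6%, which agrees with the stated figure of more than 80%.

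**3. Size of the disagreement.** Let m be the number of mismatched regions. The documents give no rate, so m is an assumption. Take all 34 regions as evaluable, with 22 TP (34 × 0.65 = 22.1).

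- PPV by wording = 22/34; PPV by formula = 22/(34 − m).
- FPR as defined in SAP 9.14.2 = (12 − m)/34.

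| m | PPV by wording (95% CI) | PPV by formula (95% CI) | Ratio 34/(34 − m) | Formula PPV + FPR |
|---|---|---|---|---|
| 0 | 64.7% (46.5–80.3) | 64.7% (46.5–80.3) | 1.00 | 100% |
| 1 | 64.7% | 66.7% (48.2–82.0) | 1.03 | 99.0% |
| 2 | 64.7% | 68.8% (50.0–83.9) | 1.06 | 98.2% |
| 4 | 64.7% | 73.3% (54.1–87.7) | 1.13 | 96.9% |

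If mismatches were instead counted as TP, PPV would be (22 + m)/34 = 67.6%, 70.6% and 76.5% for m = 1, 2 and 4. The formula is therefore too high against the worded definition, but not against every possible rule.

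**4. Effect on the 40% planning bound.** At 22 TP it is cleared under both versions. I searched for TP counts whose lower bound is at or below 40% over 34 but above 40% over 34 − m:

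- m = 1: none (19/33 has lower bound 39.2%).
- m = 2 or 3: 19 TP (37.9% for 19/34 against 40.6% for 19/32).
- m = 4: 18 or 19 TP.

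**5. Chance that the lower bound exceeds 40%.** Exact trinomial sum over 34 regions taken as independent, with P(TP) = 0.65, an assumed mismatch probability, and the rest FP. By wording: 82.6%. By formula: 85.6%, 89.8% and 96.0% for mismatch probabilities of 3%, 6% and 12%.

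**The case against.** **The literal text of Protocol 7.5.1 closes the gap.** Its two negative conditions are joined by *or*, so a region without positive histopathology is negative whatever imaging shows, and the example becomes FP. But the same reading makes every region confirmed only on imaging reference-negative, so a correctly matched region would be both TP and FP. That contradicts the use of imaging as Level 2 evidence. It cannot be the working rule, and the wording needs repair in its own right.

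**The rule may sit elsewhere.** SAP 7.8 refers programmatic detail to a supplement, and the imaging and reference-panel charters may add more. None of these is among the documents, and one of them may assign the case. The SAP describes the supplement, however, as detailing the algorithm it has just listed, and that list has no class for this region.

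**The intent can be recovered.** Wording and formula are presented as one quantity, which suggests that FP is meant to be the remainder. This supports the fix. It does not change the FP definition that a programmer would follow.

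**The effect may be small or nil.** This stands. The frequency is unknown, several conditions must coincide, SAP 4.1 plans no formal test, and at m = 1 no TP count crosses 40%. The 12% mismatch rate is only the top of an assumed range, and independence of regions is a simplification. Nor is every mismatch necessarily a localisation error: Protocol 7.5.2 itself warns that a positive follow-up scan may reflect a different disease state.

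The sizing phrase in SAP 4.2 has no evaluability condition, so it gives only weak support to the worded denominator. The FPR denominator is the stronger evidence.

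**Conclusion.** The concern holds and should be fixed. On the text of SAP 7.8 and Protocol 7.5.2, a PET-positive region whose only reference lesion is on imaging in another subregion belongs to no class, so co-primary region-level PPV has two denominators. Against the worded definition the formula can only raise the estimate: from 64.7% to 66.7%, 68.8% or 73.3% for 1, 2 or 4 mismatches among 34 evaluable positive regions with 22 TP. PPV and FPR then no longer sum to 100%.

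The participant level has no such gap, because a participant with this finding, no TP region and no confirmed PSA response is FP under SAP 7.8. The two levels would therefore treat the same finding differently.

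The size rests on an assumed mismatch count and is zero if no mismatch occurs. The 40% figure is a planning bound, crossed only in borderline results. Confidence is moderate, because the supplement could not be checked.

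**What to change.** - **SAP 7.8:** define a region-level false positive as a region that is PET-positive, has an evaluable Reference Standard and does not meet the TP criteria. This is the construction already used at participant level. TP + FP then equals the worded denominator, and PPV + FPR = 100%.
- **Supplement:** confirm that the programming document named in SAP 7.8 applies the same rule.
- **Reporting:** tabulate the number of mismatched regions by reader and by day. The subregion listings in SAP 9.12 and 9.13 let a reader find such regions but do not settle the endpoint.
- **Protocol 7.5.2 and 7.5.1:** align the FP definition, and join the two conditions for a negative region with *and* instead of *or*.

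**Cost.** Two or three sentences, one programming line and one count in a table. A change to the signed SAP before database lock needs a SAP amendment (SAP 1.0), and a Protocol change must go to the IRB (Protocol 11.9). If the Protocol is not otherwise being amended, the SAP 7.8 edit alone is enough to settle the endpoint. The reported PPV may be slightly lower than under the formula as it stands.

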## • Non-evaluable:

o A region that has either non-evaluable (NE) Cu-SAR-bisPSMA PET/CT results for a specific timepoint (Day 0 or Day 1) or has a non-evaluable or inconclusive Reference Standard will not be assigned for that timepoint.

Assessments of **Participant-Level** Reference Standard against the Cu-SAR-bisPSMA PET/CT results:

• True Positive:

September 4, 2024 CONFIDENTIAL Page 22 of 46

- A participant with at least one TP region and/or at least one unequivocal Cu-SAR-bisPSMA positive lesion in any region and a confirmed PSA response to radiation or other salvage focal therapy.
  - Confirmed PSA response following radiation or other salvage focal therapy (as long as no concomitant ADT is given) = total PSA decline ≥50% from baseline, confirmed by a 2nd value within 4 weeks per Prostate Cancer Working Group 3 criteria.

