6.2 Permitted Treatments

All SOC treatments are permitted throughout the duration of the participant's involvement in the study with the exception of those treatments outlined in Section 6.3.

6.3 **Prohibited Treatments**

Treatment with investigational agents (that are likely to affect PSA levels or antineoplastic agents), saw palmetto, estrogens, steroids, testosterone supplements, 5ARIs (finasteride/dutasteride), and any antineoplastic therapy (with the exception of radiation or other salvage focal therapy with no concomitant ADT initiated following completion of Visit 4) is prohibited throughout the duration of the participant's involvement in the study.

Histopathological confirmation of PC prior to commencement of radiation or other salvage focal therapy is strongly encouraged.

Participants who receive prohibited treatment(s) should remain in the study until completion of Visit 4 to enable the assessment of safety.

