7.1.4 Prostate Cancer Treatments

Any PC treatment that the participant receives during the study must be recorded on the eCRF.

This includes single agent or combination in order of administration, start and stop dates, dose(s), and schedule(s), the disease state in which it was administered (biochemical recurrence or M1; for M1 specify if node, visceral/soft tissue or bone), response (resistant or sensitive) on the basis of PSA if appropriate; and type of progression (PSA, radiographic [bone, nodal, visceral], clinical [e.g., pain escalation]) if applicable.

For radiation therapy, target region(s), dose (Gy) and number of fractions should be recorded.

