## • False Positive:

• A participant who does not meet the TP criteria and has at least one unequivocal Cu-SAR-bisPSMA PET-positive lesion and has an evaluable Reference Standard.

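### A PSA response to focal therapy makes a PET-positive participant true positive without any check that the treated region was PET-positive, so participant-level CDR can be biased upward

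*SAP*

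**What the plan says.** Protocol 7.5.2 matches the PET result to each kind of reference evidence at a different level. Histopathology is matched by region. The other two are set as "subregion-level matching for imaging and participant-level matching for PSA response to radiation or other salvage focal therapy".

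SAP 7.8 carries this into the participant-level TP definition. One route is a TP region. The other is an unequivocal "positive lesion in any region and a confirmed PSA response to radiation or other salvage focal therapy". The response is a PSA decline of at least 50% from baseline, confirmed within four weeks, with no concomitant ADT.

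FP is the residual class in both documents. The SAP wording begins "A participant who does not meet the TP criteria and has at least one unequivocal", and the SAP adds that the Reference Standard must be evaluable.

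Protocol 7.5.1 ranks the evidence. PSA response is Level 3, reached "OR if neither histopathology or conventional imaging are available or informative". SAP 9.14.3.2 defines Level 3 consistently with this, as PSA response with no contribution from histopathology or imaging.

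Protocol 6.3 prohibits antineoplastic therapy on study "with the exception of radiation or other salvage focal therapy with no concomitant ADT initiated following completion of Visit 4", and adds: "Histopathological confirmation of PC prior to commencement of radiation or other salvage focal therapy is strongly encouraged". Protocol 7.1.4 says: "For radiation therapy, target region(s), dose (Gy) and number of fractions should be recorded".

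**The concern.** Every participant enters with PSA-defined recurrence and negative or equivocal conventional imaging, so recurrent disease somewhere is already likely. A PSA fall after focal therapy supports disease in the treated field. It says nothing about a PET lesion outside that field.

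Suppose a central reader marks only a rib lesion, the prostate bed is irradiated, and PSA halves. Under the PSA route that scan is TP, although the response points to a site the reader called negative.

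The post-scan management plan rests on the unblinded local interpretation (Protocol 7.3.2.1 and 7.5.3), whereas TP is assigned separately for each blinded central reader (Protocol 10.4.5.1). A central reader who missed the treated site and marked another gets the same participant-level TP as one who marked the treated site.

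At stake are participant-level CDR (a co-primary endpoint), participant-level PPV and FPR, and composite CDR. Compared with a matched rule, the unmatched rule can only add TPs.

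**Working it through.** **1. The rules side by side**

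| Evidence | Location condition for TP | Source |
|---|---|---|
| Histopathology | Same region | Protocol 7.5.2, SAP 7.8 |
| Conventional imaging | Same subregion | Protocol 7.5.2, SAP 7.8 |
| PSA response to focal therapy | None | Protocol 7.5.2, SAP 7.8 |

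The hierarchy limit is in Protocol 7.5.1 only. The participant-level TP rule joins its two routes by and/or, and FP applies only when TP fails. Read literally, a PSA response therefore overrides negative follow-up imaging. Section 7.5.1 does not settle this: it says that negative histopathology passes down to imaging, but not whether a negative scan counts as informative.

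**2. The plan's own sizing figure (Protocol 10.3, SAP 4.2)**

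Inputs: n = 40 evaluable, assumed CDR 42%, lower limit of the two-sided 95% Clopper-Pearson interval to exceed 20%.

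- 13/40 has lower limit 18.6% and 14/40 has 20.6%, so at least 14 TPs are needed.
- P(X ≥ 14 | n = 40, p = 0.42) = 85.5%, which agrees with the stated power of more than 85%.
- 40/(1 − 0.20) = 50 enrolled, as stated.

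The sample-size figures are not in error.

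**3. Effect on CDR (assumed counts)**

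Start from the planning case: 0.42 × 40 = 16.8, taken as 17 TPs. Let k be the number of TPs that rest only on a PSA response to an unmatched treated region. The documents give no rate of focal therapy, PSA response or mismatch, so k = 0 to 4 is an assumption.

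Without the unmatched TPs, a case becomes one of two things:

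- Non-evaluable, if neither histopathology nor imaging is informative. It leaves the denominator: CDR = (17 − k)/(40 − k).
- FP, if informative imaging or histopathology was negative. It stays in the denominator: CDR = (17 − k)/40.

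| k | Non-evaluable: CDR (lower limit) | FP: CDR (lower limit) |
|---|---|---|
| 0 | 17/40 = 42.5% (27.0%) | 17/40 = 42.5% (27.0%) |
| 2 | 15/38 = 39.5% (24.0%) | 15/40 = 37.5% (22.7%) |
| 4 | 13/36 = 36.1% (20.8%) | 13/40 = 32.5% (18.6%) |

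The upper limit at k = 0 is 59.1%. One unmatched case changes CDR by 1.5 points if it becomes non-evaluable (16/39 = 41.0%) and by 2.5 points if it becomes FP (16/40 = 40.0%).

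**4. Participant-level PPV in the same case**

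Protocol 10.3 assumes 65% PET-positive, which is 0.65 × 40 = 26 participants. PPV is then 17/26 = 65.4%. With k = 2 it is 15/24 = 62.5% (non-evaluable) or 15/26 = 57.7% (FP). With k = 4 it is 13/22 = 59.1% or 13/26 = 50.0%.

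**5. Region-level PPV**

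The region-level TP rules use histopathology and imaging only, so a PSA response cannot make a region TP and this endpoint does not move.

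**The case against.** The strongest reply is the hierarchy in Protocol 7.5.1. Follow-up conventional imaging is required for everyone around Day 90, and again around Day 180 if the first is negative or equivocal. Histopathology before focal therapy is encouraged. PSA is thus meant as a last resort, and the rib example arises only when imaging was uninformative. This stands as a narrowing. It does not remove the problem: genuine Level 3 cases have no other localising evidence, and the TP and FP definitions omit the limit.

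Other replies have partial weight.

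- Participant-level matching for PSA is explicit, so it looks deliberate, and localisation has its own co-primary endpoint in region-level PPV, reported by reader. That limits how far differences between readers are hidden. It does not make CDR a measure of correct detection in unmatched cases.
- SAP 9.14.3.2 summarises CDR and participant-level PPV by level of evidence. This shows how many cases are Level 3, but not whether the treated region was PET-positive. The sensitivity analyses in SAP 9.14.1.1 cover only missing, non-evaluable or inconclusive reference data.
- If therapy follows the local PET reading, overlap with PET-positive sites is likely, so k may be small or zero.
- The programming supplement named in SAP 7.8 and the panel charter are not available here and may hold a location rule. None is in the protocol or SAP.

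Someone reading the TP rule alone might infer that empirical treatment routinely turns false-positive scans into correct detections, and that removing such cases would make the trial miss its 20% target. The documents support neither. Under the hierarchy most such cases are unverified, not shown to be false. The lower limit falls below 20% in the table only if four TPs are unmatched and all four become FP on informative evidence, which is what the hierarchy is meant to keep out of Level 3. SAP 4.1 also plans no formal hypothesis test, so 20% is a sizing figure and not a success criterion.

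**Conclusion.** The point holds in a limited form. As written, Protocol 7.5.2 and SAP 7.8 can credit a PET finding that the PSA response does not verify. The bias is upward for participant-level CDR, participant-level PPV and composite CDR, and downward for participant-level FPR.

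The size cannot be derived from the documents. With 2 to 4 unmatched TPs out of 17, CDR falls by 3.0 to 6.4 points if they become non-evaluable, and by 5.0 to 10.0 points if they become FP. The first is the relevant range if the hierarchy is enforced; the second needs the literal reading in which PSA overrides negative imaging. If every treated field overlapped a PET-positive region, the effect would be nil. The separate inconsistency between Protocol 7.5.1 and the TP/FP rules needs correcting whatever the count.

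**What to change.** 1. Reconcile Protocol 7.5.1 and 7.5.2 with the TP and FP definitions in SAP 7.8, so that the evidence hierarchy applies inside the algorithm. State whether a negative follow-up scan counts as informative.
2. Count a PSA-route TP only if a recorded treatment target region overlaps a region that is PET-positive for that central reader and timepoint. Otherwise classify the participant on histopathology or imaging, or as non-evaluable if neither is informative. At minimum, add a supportive CDR and participant-level PPV without unmatched PSA-only TPs, by reader and timepoint.
3. For non-radiation focal therapy, take the treated region from the treatment records, since Protocol 7.1.4 asks for target regions only for radiation.

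Cost: wording in both documents and one further condition in the matching, which is already done by statistical programming. Some treated regions for non-radiation therapy may have to be looked up retrospectively, because imaging data were already being collected by February 2023 (SAP 7.7). CDR may be slightly lower or rest on fewer evaluable participants.
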